3.2.7 Exclusion Criteria

3.2.7.1 Patients with $>$ Grade 2 neuropathy according to the Modified (“Balis”) Pediatric Scale (see [Section 5.2.4](#)) of Peripheral Neuropathies will be excluded except in cases in which neuropathy is secondary to prior surgery.

3.2.7.2 Patients who have previously received CDX-011 (CR011-vcMMAE; CDX-011) or other MMAE-containing agents.

3.2.7.3 Patients who have received other investigational drugs within 2 weeks or 5 half-lives (whichever is longer) prior to study enrollment.

3.2.7.4 Patients with a history of allergic reactions attributed to compounds of similar composition to dolastatin or auristatin. Compounds of similar composition include Auristatin PHE as an anti-fungal agent, Auristatin PE (TZT-1027, Soblidotin, NSC-654663) as an anti-tumor agent and symplostatin 1 as an anti-tumor agent.

3.2.7.5 Patients with known central nervous system metastasis are not eligible.

3.2.7.6 Patients who have had major surgery within 2 weeks prior to enrollment are not eligible. Procedures such as placement of a central vascular catheter, or limited tumor biopsy, are not considered major surgery.

3.2.7.7 Pregnancy and Breast Feeding

- 3.2.7.7.1 Female patients who are pregnant are ineligible since there is yet no available information regarding human fetal or teratogenic toxicities.
- 3.2.7.7.2 Lactating females are not eligible unless they have agreed not to breastfeed their infants.
- 3.2.7.7.3 Female patients of childbearing potential are not eligible unless a negative pregnancy test result has been obtained.
- 3.2.7.7.4 Sexually active patients of reproductive potential are not eligible unless they have agreed to use an effective contraceptive method for the duration of their study participation and for 2 months after the end of study treatment.

3.2.8 Regulatory Requirements

- 3.2.8.1 All patients and/or their parents or legal guardians must sign a written informed consent.
- 3.2.8.2 All institutional, FDA, and NCI requirements for human studies must be met.

4.0 TREATMENT PROGRAM

Timing of protocol therapy administration, response assessment studies, and surgical interventions are based on schedules derived from the experimental design or on established standards of care. Minor unavoidable departures (up to 72 hours) from protocol directed therapy and/or disease evaluations (and up to 1 week for surgery) for valid clinical, patient and family logistical, or facility, procedure and/or anesthesia scheduling issues are acceptable (except where explicitly prohibited within the protocol).

4.1 Overview of Treatment Plan

This is a single arm Phase 2 study to evaluate the use of CDX-011, an ADC directed against GPNMB. All subjects will receive CDX-011 at 1.9 mg/kg intravenously over 90 minutes every 21 days. Treatment will be discontinued if there is evidence of progressive disease or drug related toxicity that requires removal from therapy, as defined in [Section 5.0](#). Therapy may otherwise continue for a maximum duration of 14 months or ~18 cycles, whichever occurs first. Radiographic imaging assessments of disease status obtained after Cycles 2, 4 and 6 will be compared to imaging done just prior to initiating therapy. For those patients remaining on protocol therapy, subsequent imaging studies for assessment of disease status will occur after every 3rd cycle.

Other therapy: Although not encouraged, subjects who achieve a partial response after Cycle 2 that is confirmed after Cycle 6 will be allowed to undergo resection of sites of disease or radiation and remain on protocol therapy. Therapy will be held during surgery and resumed when recovered from surgery but at least 2 weeks after surgery. CDX-011 therapy will be held during radiation and may be resumed upon completion of the radiation treatment course. If the patient has not recovered from surgery within 6 weeks the patient will go off protocol therapy. Surgery or radiation performed on any site of measurable disease before the end of the sixth cycle will render the patient inevaluable for disease control assessment and they will be removed from protocol therapy.

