The prognosis of patients with recurrent or refractory osteosarcoma remains poor, with 10-year overall survival rates around 20%. Given the continued poor prognosis in this group of patients, novel treatment strategies are needed. There are no standard chemotherapeutic agents or targeted therapies proven to prolong survival in recurrent osteosarcoma. Glycoprotein non-metastatic B (GPNMB) is a type I transmembrane glycoprotein that is normally expressed in a variety of cell types including osteoblasts and osteoclasts, dendritic cells, macrophages, hematopoietic cells, melanocytes and keratinocytes. Aberrant and over expression of GPNMB has been demonstrated in a variety of cancers including osteosarcoma. GPNMB is predominantly expressed on the cell surface of malignant cells, whereas in normal tissues it is generally restricted to intracellular compartments. This unique expression pattern makes GPNMB an attractive target for antibody drug conjugate (ADC) targeted therapy. CDX-011 is an ADC directed against GPNMB. It is comprised of a fully-human IgG2 monoclonal antibody (CR011) conjugated to the potent microtubule inhibitor, monomethyl auristatin E (MMAE), via a protease-sensitive valine-citrulline peptide linker and p-aminobenzoic acid (PABA) spacer. CDX-011 is theorized to exert its antitumor activity by selectively delivering the potent cytotoxin MMAE to GPNMB-expressing tumor cells. Pre-clinical data suggest that CDX-011 may have anti-tumor activity in osteosarcoma. In this Phase 2 study, eligible patients between the ages of 12 months and 50 years with unresected, recurrent or refractory osteosarcoma will receive CDX-011, administered once every 21 days for up to 14 months. Progression free survival and response to therapy will be assessed. In addition, the tolerability and pharmacokinetic (PK) disposition of CDX-011 will be evaluated.

EXPERIMENTAL DESIGN SCHEMA

*Glembatumumab vedotin will be given on Day 1 of each 21-day cycle

Note: Patients who undergo surgical resection of or radiation to any site of measurable disease prior to completion of the 6th cycle of therapy will be taken off protocol therapy.

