9.2 Study Design

Feasibility Cohort: The first six (6) younger patients (< 18 years of age) who are evaluable for toxicity will be considered as the feasibility cohort. All such patients will be assigned to receive 1.9 mg/kg/dose. Enrollment to this cohort will not be segregated by prior treatment with eribulin. Study accrual will be suspended after the sixth patient is enrolled; enrollment of patients 18 years of age or older will continue regardless of the result in the feasibility cohort. If dose limiting toxicity (DLT) during the first cycle of therapy occurs in one or fewer evaluable patients then the trial accrual will proceed as outlined below. Patients who are enrolled in the toxicity cohort who receive the “feasible” dose of CDX-011 will be considered in the outcome evaluation rules presented below for the relevant patient stratum as it relates to prior eribulin exposure.

Patients will be enrolled in two stages. In the first stage, 19 disease control and RECIST response evaluable patients will be enrolled. Each patient will be evaluated for both outcome measures: (1) disease control success; and (2) RECIST response (CR or PR v. not CR or PR). The decision rule for the two stage study design is summarized as:

Stage	Number of Patients Enrolled in Stage	Cumulative Response Results	Decision
I	19	4 or fewer disease control successes	Terminate the trial with the conclusion that Glembatumumab

		and 1 or fewer RECIST responders	Vedotin is not associated with sufficient activity for further single agent investigation
		5 or more disease control success or 2 or more RECIST responders	Continue to stage II
II	10	8 or fewer disease control successes and 4 or fewer RECIST responders	Terminate the trial with the conclusion that Glembatumumab Vedotin is not associated with sufficient activity for further single agent investigation
		9 or more disease control successes or 5 or more RECIST responders	Terminate the trial with the conclusion that Glembatumumab Vedotin is associated with sufficient activity for further single agent investigation

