9.4 Evaluability for Disease Control and Response

Which Patients will be Considered Evaluable for RECIST Response:

Any eligible patient who receives at least one dose of CDX-011 will be considered evaluable for response with the following exception: if a patient receives non-protocol anti-cancer therapy during the response evaluation period after the patient is considered as having a partial or complete response but prior to confirmation of this status by tumor imaging and before progressive disease is noted, the individual will be considered inevaluable for the response endpoint. Further, patients who stop CDX-011 after the 1st evaluation because of toxicities or death will be considered evaluable for the response evaluation and will be counted as non-responders for the response endpoint.

Which Patients Will Be Considered Evaluable for Disease Control Success:

Any eligible patient who receives at least one dose of CDX-011 will be considered evaluable for response with the following exception: if a patient receives non-protocol anti-cancer therapy during the first four months of therapy or first six cycles of therapy, whichever occurs first, is considered as having a partial or complete response but prior to confirmation of this status by tumor imaging and before progressive disease is noted, the individual will be considered inevaluable for the disease control success endpoint.

Which Patients Will be Considered a Disease Control Success:

Any patient who is evaluated free of all detectable disease (complete response) or is considered as having a partial response or is considered as having stable disease ('at least stable disease') after four months of therapy or at the end of the sixth cycle, whichever occurs first.

Which Patients Will be Considered Not a Disease Control Success:

Any evaluable patient who does not meet the criteria for disease control success (complete response, partial response or stable disease) will be considered to not have experienced disease control success.

In particular, any patient who dies because of treatment-related toxicity during the first six cycles of therapy and within the first four months since starting treatment will be

considered not to have experienced disease control success. Also, any patient who is eligible, receives one dose of CDX-011 and is lost to follow-up at (for example) the end of cycle 2 will be considered not a disease control success (complete response, partial response or stable disease).

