Patients who are not evaluable for both disease control and response evaluation may be replaced for the purposes of the statistical rule.

9.5 **Evaluability for Toxicity**

Tolerability of CDX-011 - An eligible patient will be considered for toxicity monitoring if one of the following occurs: (1) complete one cycle of CDX-011 prior to receiving non-protocol anticancer therapy; (2) die on protocol therapy for a reason considered possibly, probably or likely related to CDX-011; or (3) are removed from protocol therapy because of an adverse experience possibly, probably or likely related to CDX-011. A toxicity-evaluable patient will be considered in the analysis during the interval from study enrollment until the termination of protocol therapy. A toxicity-evaluable patient will be considered to have experienced an excessive toxicity event if: (1) the patient dies on protocol therapy for a reason considered possibly, probably or likely related to; or (2) experiences a dose-limiting toxicity (DLT). DLTs will be as defined in [Section 5.1.1](#) of the protocol:

The analytic unit for monitoring for excessive toxicity will be the patient-cycle: Each cycle where the patient receives CDX-011 and does not receive non-protocol anticancer therapy will be considered in the analysis. If there is overwhelming evidence that the dose selected for this trial has a per-cycle-DLT probability of more than 30%, we will identify the regimen to the COG DSMC, Bone Tumor Committee leadership and CTEP as associated with a toxicity profile that may require modification of the regimen. We will use a Bayesian rule to monitor for excessive toxicity. We will assume a beta prior to distribution with $\alpha=0.6$ and $\beta=1.4$. If this posterior probability of the chance of DLT is at least 30% exceeds 80%, we will identify the regimen to the COG DSMC, Bone Tumor leadership and CTEP as associated with a toxicity profile that may require modification of the regimen.

9.6 **Estimation of Disease Control and RECIST Response Rates**

$P(R)$ and $P(S)$ for each cohort defined by prior eribulin exposure will be estimated using the maximum likelihood estimates, *viz.*,

$$P(R) \hat{=} \hat{p}_R = \frac{\text{Number of Patients Considered as PR or CR}}{\text{Number of Evaluable Patients in Cohort}};$$

$$P(S) \hat{=} \hat{p}_S = \frac{\text{Number of Patients With Disease Control at 4 Months}}{\text{Number of Evaluable Patients in Cohort}}$$

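### Sections 4.1 and 9.4 disagree on whether early surgery or radiation removes a patient from the disease-control analysis, and the 9.4 toxicity/death sentence has no exception for a confirmed response

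*Combined protocol and SAP*

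**What the plan says.** **Early local therapy.** Section 4.1 (Other therapy) states that surgery or radiation on any site of measurable disease "before the end of the sixth cycle will render the patient inevaluable for disease control assessment". It sets no condition on response status. The Experimental Design Schema note says only that such patients "prior to completion of the 6th cycle of therapy will be taken off protocol therapy". The note in the Therapy Delivery Map (4.2.1) and criterion (h) of 8.1 likewise deal only with removal from therapy. Section 4.1 alone attaches inevaluability.

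Section 9.4 starts from the opposite default: an eligible patient with one dose is evaluable, with one exception. For disease control the exception applies "if a patient receives non-protocol anti-cancer therapy during the first four months of therapy or first six cycles of therapy, whichever occurs first", and the sentence then runs on: "whichever occurs first, is considered as having a partial or complete response but prior to confirmation of this status by tumor imaging". A further condition is that progression has not yet been recorded. An evaluable patient who does not meet the success criteria is coded as not a success. As an illustration, a patient who "is lost to follow-up at (for example) the end of cycle 2 will be considered not a disease control success".

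**Replacement.** Section 9.4 closes: "Patients who are not evaluable for both disease control and response evaluation may be replaced for the purposes of the statistical rule". Section 9.2 says that in stage I "19 disease control and RECIST response evaluable patients will be enrolled". The final rule declares activity on "9 or more disease control successes or 5 or more RECIST responders" among 29.

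**Toxicity and death.** Under RECIST response, 9.4 keeps patients who stop CDX-011 for toxicity or death after the first evaluation in the denominator and codes them as non-responders. It sets no upper time limit and makes no exception for a response already confirmed.

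**The concern.** Both endpoints feed hard cut-offs in a single-arm trial, so each patient needs one evaluability status and one code per endpoint, fixed before results are seen. Here two sections give different answers for the same patient on disease control, and a third rule can contradict the definition of a responder. If this is settled case by case after outcomes are known, the choice can influence the verdict.

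On disease control, a patient who leaves therapy early for local treatment either disappears and may be replaced by someone with a fresh chance of success (4.1), or stays as a failure (9.4). On response, a patient with a confirmed PR who later stops for toxicity is a responder under 9.2, 9.6 and 10.2.3.3, and a non-responder under the literal text of 9.4.

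**Working it through.** **Where the sections conflict (a).** I take surgery and radiation to be non-protocol anti-cancer therapy; 9.4 does not say so.

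| Status at local therapy before end of Cycle 6 | 4.1 | 9.4 |
|---|---|---|
| CR/PR not yet confirmed | inevaluable | inevaluable |
| Stable disease | inevaluable | evaluable |
| No assessment yet | inevaluable | evaluable |

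In 9.4, success means CR, PR or stable disease after four months of therapy or at the end of the sixth cycle, whichever is first. Sections 4.1 and 8.1 take these patients off therapy before Cycle 6 ends, so most cannot qualify, and 9.4 then codes them as not a success. The contrast to compute is therefore drop-and-replace against keep-as-failure.

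**Reproducing the design table.** Inputs from 9.2: 19 then 10 patients; continue if S ≥ 5 or R ≥ 2; effective if S ≥ 9 or R ≥ 5 of 29; Pr(S|R) = 0.90. Each patient falls in one of four cells:

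- S and R: 0.9·P(R)
- S only: P(S) − 0.9·P(R)
- R only: 0.1·P(R)
- neither: the remainder

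At (P(S), P(R)) = (0.20, 0.05) the cells are 0.045, 0.155, 0.005, 0.795. At (0.42, 0.05) they are 0.045, 0.375, 0.005, 0.575. Exact enumeration gives P(effective) of 0.108, 0.949, 0.904 and 0.789 at (0.20, 0.05), (0.42, 0.22), (0.42, 0.05) and (0.20, 0.22). The plan states 0.11, 0.95, 0.904 and 0.79, so its table reproduces.

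**Part (a), with an assumed share f = 0.10 affected.** The documents give no frequency, so two extremes bracket the prognosis of those affected.

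- *All would be failures.* Drop and replace: take f from the neither cell and divide all cells by 1 − f. At the null, P(S) = 0.20/0.9 = 0.222 and P(R) = 0.05/0.9 = 0.056. Keep: nothing changes.
- *All would be stable-disease successes.* Drop and replace: take f from the S-only cell and divide by 1 − f. At the null, P(S) = (0.20 − 0.10)/0.9 = 0.111 and P(R) = 0.056; at (0.42, 0.05), P(S) = 0.32/0.9 = 0.356. Keep as failure: move f from S-only to neither, so P(S) = 0.10 or 0.32 and P(R) = 0.05.

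| P(effective) | Drop and replace (4.1) | Keep as failure (9.4) |
|---|---|---|
| (0.20, 0.05), all failures | 0.175 | 0.108 |
| (0.20, 0.05), all stable-disease successes | 0.022 | 0.014 |
| (0.42, 0.05), all failures | 0.963 | 0.904 |
| (0.42, 0.05), all stable-disease successes | 0.734 | 0.590 |

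The direction is the same in every row, and must be: replacement exchanges a certain non-success for a patient who may succeed. If dropped patients are not replaced but still fill places in the 19 and 29, the counts against the cut-offs equal those under keep-as-failure. Only the 9.6 estimate moves; for example, 8/29 = 27.6% becomes 8/27 = 29.6% with two dropped.

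**Part (b).** Scheduled scans follow Cycles 2, 4 and 6. A PR after Cycle 2 that is seen again after Cycle 4 (2 × 21 = 42 days later) meets the four-week confirmation in 10.2.3.3. If that patient then stops for toxicity:

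- 9.2: R is met, because the first CR/PR was recorded by the end of Cycle 6.
- 9.6: counted in the numerator, as a patient considered PR or CR.
- 10.2.3.3: best response up to progression is PR.
- 9.4, read literally: non-responder.

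With an assumed share f of responders recoded, P(R) = 0.22(1 − f), which is 0.198 or 0.176 for f = 0.10 or 0.20, and P(S) is unchanged:

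| Power | f = 0 | f = 0.10 | f = 0.20 |
|---|---|---|---|
| (0.20, 0.22) | 0.789 | 0.698 | 0.588 |
| (0.42, 0.22) | 0.949 | 0.940 | 0.931 |

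**The case against.** The strongest reply is that 9.4 is the statistical section, its default is clear, and it already codes patients who do not meet success. Most of this stands. It means that counting early local-therapy patients as failures is not a new rule. No text, however, says that 9.4 overrides 4.1, and the 9.4 exception is itself broken: beside the parallel response sentence, it has lost the words that tie the therapy to the time after a response is noted. The intended wording can be read from that parallel.

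Other replies also carry weight:

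- Local therapy is described as not encouraged, early use ends protocol therapy, and nothing supports 10% in particular. The figures show sensitivity; they are not forecasts.
- Read with 9.2, the replacement sentence most naturally covers anyone not evaluable on both endpoints. It needs clarifying but is not a contradiction.
- The toxicity sentence may be meant only to keep early stoppers in the denominator. For patients who stop between the first and second scheduled evaluations no response can yet be confirmed, so coding them as non-responders agrees with 10.2.3.3. The contradiction arises only for later stops after confirmation.
- The time windows differ little: four months is about 122 days and six cycles are 6 × 21 = 126.

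A reader might extend (a) to patients whose response was already confirmed at local therapy. That case is weak, because 4.1 itself speaks of a partial response after Cycle 2 being confirmed after Cycle 6.

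**Conclusion.** The concern holds as two wording defects that bear on the primary counts. In (a), 4.1 and 9.4 conflict for patients with stable disease or no assessment at early local therapy. Relative to 9.4, dropping and replacing raises the chance of an effective verdict: by 0.067 (0.175 − 0.108) or 0.008 (0.022 − 0.014) at the null rates, and by 0.059 (0.963 − 0.904) or 0.144 (0.734 − 0.590) at (0.42, 0.05). These differences assume 10% affected, replacement, and the natural reading of 9.4. If four months were read as time since starting treatment, some of these patients could still count as successes under 9.4.

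In (b), the literal sentence would cost 0.091 or 0.201 of power at (0.20, 0.22) for 10% or 20% of responders recoded, and 0.009 or 0.018 at (0.42, 0.22). It matters mainly for a drug that works through response without added disease control.

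Three stronger inferences are not supported. The design table is not wrong; it reproduces. The trial's false-positive rate is not shown to be 0.175, since no frequency is given. And the fall from 0.904 to 0.734 is not a loss caused by choosing 4.1: it compares 4.1 with a trial without local therapy, whereas 9.4 in the same scenario gives 0.590. Because the event frequency is unknown, severity is minor to moderate.

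**What to change.** Before outcomes are known:

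1. Reconcile the evaluability statement in 4.1 with 9.4 so that one analysis rule applies. Keep the 9.4 default: eligible dosed patients stay in the denominator, and those not meeting success count as not a success.
2. Repair the 9.4 disease-control exception so that it matches the parallel response sentence.
3. State at the end of 9.4 that a patient inevaluable on either endpoint is replaced, consistent with 9.2.
4. Amend the toxicity/death sentence so that these patients are non-responders unless a CR or PR was documented and confirmed before stopping.

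The cost is wording in 4.1 and 9.4, with no new data. On the natural reading, item 1 adds no power loss beyond what 9.4 already implies, and item 4 brings the response count into line with 9.2, 9.6 and 10.2.3.3. These are analysis rules only; no clinical rule on surgery, radiation or stopping treatment is proposed.

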4.1.1 Concomitant Therapy

4.1.1.1 CYP3A4 inducers and inhibitors

The use of the following medications should be discontinued prior to initiation of protocol therapy and should be avoided during protocol therapy if reasonable alternatives exist. This is not an inclusive list; please refer to other resources such as <http://medicine.iupui.edu/clinpharm/ddis/table.aspx> or other frequently updated medical reference for additional information.

CYP3A4 substrates	Strong Inhibitors*	Moderate Inhibitors	Weak Inhibitors	Inducers
alfentanil	atazanavir	aprepitant	amiodarone	armodafinil
amiodarone	boceprevir	atazanavir	ciprofloxacin	barbiturates
aprepitant	clarithromycin	cimetidine	doxycycline	bosentan
benzodiazepines	cobicistat	crizotinib	mifepristone	carbamazepine
bortezomib	conivaptan	cyclosporine	metronidazole	deferasirox
brentuximab	delavirdine	desipramine	nicardipine	efavirenz
budesonide	fosamprenavir	diltiazem	propofol	etravirine
calcium channel blockers	indinavir	erythromycin	quinidine	fosphénytoïne

cisapride	itraconazole	fluconazole	sertraline	glucocorticoids
citalopram/escitalopram	ketonconazole	fluvoxamine	tacrolimus	modafinil
glucocorticoids	nefazodone	fosaprepitant		nafcillin
crizotinib	nelfinavir	grapefruit		nevirapine
cyclosporine	posaconazole	grapefruit		oxcarbazepine
cyclophosphamide	ritonavir	juice		phenobarbital
dapsone	saquinavir	imatinib		phenytoin
dasatinib	telaprevir	norfloxacin		pioglitazone
dihydroergotamine	telithromycin	tetracycline		primidone
docetaxel	voriconazole	verapamil		rifabutin
doxorubicin				rifampin
ergotamine				rifapentine
erlotinib				ritonavir
esomeprazole				St. John's wort
estrogens				topiramate
etoposide				
fentanyl				
fosaprepitant				
gefitinib				
haloperidol				
HIV antiretrovirals				
HMG Co-A inhibitors				
ifosfamide				
imatinib				
irinotecan				
itraconazole				
ketoconazole				
lansoprazole				
lapatinib				
losartan				
lovastatin				
macrolide antibiotics				
medroxyprogesterone				
methadone				
midazolam				
modafinil				
monteleukast				
nefazodone				
nilotinib				
omeprazole				
ondansetron				
paclitaxel				
pazopanib				
quinidine				
sildenafil				
sirolimus				
sunitinib				
tacrolimus terfenadine				
telaprevir				
tamoxifen				

temsirolimus				
teniposide				
trimethoprim				
vinca alkaloids				
zolpidem				

* Certain fruits and fruit juices (star fruit, Seville oranges, pomegranate) may inhibit CYP 3A4 isozyme, however, the degree of that inhibition is unknown.

4.1.1.2 The administration of P-gp inhibitors should be avoided while the patient is receiving protocol therapy due to risk of increased exposure to MMAE.

4.1.1.3 No other antineoplastic agents may be given while the patient is receiving protocol therapy.

4.1.1.4 Growth factors that support white cell number or function should only be administered for culture proven bacteremia, invasive fungal infection, or if there was a Grade 4 ANC of > 7 days duration in a previous cycle or a delay of > 14 days between cycles for neutropenia.

For COG Supportive Care Guidelines see:

https://members.childrensoncologygroup.org/prot/reference_materials.asp under Standard Sections for Protocols.

